6.6 Ongoing Assessment and Outcome

Adverse events will be assessed at all postop visits until resolution or stabilization occurs. Changes in severity and intervention will be recorded.

The clinical outcome of an AE will be characterized as follows:

- Resolved without sequelae
- Resolved with sequelae (specify)
- Stabilization; no possible resolution
- Ongoing (i.e. continuing at time of study discontinuation)
- Death.

After exit from the study, ongoing AEs should be followed until resolution (with or without sequelae), stabilization, or it is determined that there is no possible resolution. Subjects who present or report with a significant, ocular (study eye only) adverse event at the exit visit, should be followed by the physician after exit for AE resolution/stabilization.

6.7 Treatment or Action Taken

- None
- Medical Intervention
- Surgical Intervention (includes device explant)
- Other.

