5.2 Study Populations

The **Effectiveness Population** will consist of all the subjects who undergo the Hydrus implantation surgery and are not discontinued early from the study due to unrelated reasons such as death or relocation. The primary analyses on the primary and secondary effectiveness endpoints will be based on the **Effectiveness Population**. The reasons for discontinuation will be reported.

Intent to Treat. The ITT population will include all subjects undergoing Hydrus Microstent implantation surgery. For this study the ITT population is the safety population.

Per Protocol. The Per Protocol (PP) population will include all implanted subjects who meet the following criteria:

- Subject meets all protocol eligibility criteria.
- Subject completes the 12-month visit.
- Subject received secondary surgical intervention (SSI) for controlling IOP will be included and treated as non-responder
- Subjects without adverse events that lower IOP such as cyclodialysis cleft.
- Additional criteria, if any, will be established before the data review and database closure.

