5.3 Effectiveness Endpoints Analyses

5.3.1 Primary Effectiveness Endpoint

The primary effectiveness outcomes for this study is:

- Proportion of subjects with $\geq 20\%$ decrease in mean diurnal IOP at 12 months while maintaining the same or fewer number of medications as at baseline

The primary analyses of the primary endpoint will be based on the Effectiveness Population. The exact 95% confidence interval of the response rate will be calculated based on binomial distribution.

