- Flat anterior chamber with lens/cornea touch or shallow anterior chamber with peripheral iridocorneal apposition
- Hyphema ≥ 2 mm in height (layered) at any time
- Hyphema present or arising > 30 days postoperative
- Hypotony (defined as IOP < 6 mmHg) onset before 1-month postoperative
- Hypotony (defined as IOP < 6 mmHg) onset at or after 1-month postoperative
- Implant corneal touch
- Implant-iris touch associated with intraocular inflammation, pigment dispersion, or other sequelae
- Inadvertent bleb
- Increase in vertical C/D ratio of ≥ 0.3 units from screening on fundus examination
- Iris prolapse/wound incarceration
- Maculopathy including hypotonic maculopathy
- Persistent diplopia
- Pupil block
- Retinal complications (e.g., flap tears, retinal break, retinal detachment, age related macular degeneration, diabetic retinopathy, macular edema, epiretinal membrane, central serous retinopathy, or proliferative vitreoretinopathy)
- Scleral ectasia
- Surgical re-intervention in the study eye (other than paracentesis to relieve pressure within the 1 week visit)
- Toxic anterior segment syndrome (TASS)
- Vitreous haze
- Vitreous hemorrhage
- Vitritis
- Worsening of 2-points (from screening) to "severe" on the slit lamp examination findings (other than cells and flare) onset at or after 3-months postoperative not associated with a pre-existing condition
- Worsening of lens opacities (defined as a 2.0 or more score change on at least one category of the LOCS III grading system, at 2 or more consecutive visits)
- Worsening of visual field (mean deviation worsening by 3.0 dB or more, confirmed by 2 repeat measurements)
- Wound dehiscence (persistent aqueous leak or fistula formation)

For any adverse event that may be due to incorrect device positioning (i.e. vitreous hemorrhage, hyphema, hypotony), gonioscopy should be performed to assess the device position. If the position cannot be adequately evaluated by gonioscopy, ultrasound biomicroscopy (UBM) should be performed.

For slit lamp examination, gonioscopy and fundus findings for which there is no grading scale, any finding considered by the study investigator to be marked or severe, i.e., clinically significant, should be recorded as an Adverse Event.

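### The primary analysis can score an eye as a Hydrus responder after its microstent has been explanted for a reason other than IOP control

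*Combined protocol and SAP*

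**What the plan says.** Section 5.3.1 defines a responder as a subject with at least a 20% "decrease in mean diurnal IOP at 12 months while maintaining the same or fewer number of medications as at baseline". It sets no condition that the device is still in the eye and has no surgical failure clause. It adds: "The primary analyses of the primary endpoint will be based on the Effectiveness Population".

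Section 5.2 defines that population as all "subjects who undergo the Hydrus implantation surgery and are not discontinued early from the study due to unrelated reasons such as death or relocation". An explanted eye is not excluded by this wording.

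The only rule that turns surgery into non-response is also in section 5.2, but in the list of Per Protocol criteria: "Subject received secondary surgical intervention (SSI) for controlling IOP will be included and treated as non-responder". SSI is not defined further.

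Explantation appears once, in section 6.7, among the actions taken for an adverse event: "Surgical Intervention (includes device explant". Section 6.8.1 lists a related anticipated event, "Surgical re-intervention in the study eye (other than paracentesis to relieve pressure within the 1 week visit". Neither entry is tied to an effectiveness rule.

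**The concern.** Every subject in the primary analysis has Hydrus surgery, and the result is one proportion with an exact interval. A reader will take that proportion as the share of eyes in which the device worked. If the device has been taken out because of a complication, the 12-month pressure was measured in its absence, yet the rule as written can still credit it to the device.

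The plan's own SSI rule shows that the sponsor regards some later surgery as failure. As written, an eye's classification depends on the reason given for the surgery and on which population is analysed. If this is not settled in advance, it will be settled after the pressures are known. The secondary endpoint in section 5.3.2 has the same gap, because IOP measured after explantation enters the mean change unmarked.

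**Working it through.** The documents state no sample size, assumed response rate, performance goal or explant rate, so there is no figure of the plan's own to reproduce. The check is first one of wording, then an illustration of size.

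**Step 1: follow one eye through the rules.** Suppose a microstent is explanted during follow-up because of an event such as "Implant corneal touch" (section 6.8.1). That this event would lead to removal is my inference. That removal is foreseen at all is stated in section 6.7. At month 12 the diurnal IOP is at least 20% below baseline and no medication has been added.

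| Rule | Where | Does it make the eye a non-responder? |
|---|---|---|
| Responder definition | 5.3.1 | No. Only IOP and medication count are tested, and both are met. |
| Effectiveness Population | 5.2 | No. The eye was operated on and the subject did not leave early for an unrelated reason. |
| SSI rule | 5.2, Per Protocol list | No. The removal was not done to control IOP, and the rule is not written for the primary population. |
| Footnote 6 to the visit schedule | 4.0 | No. It concerns subjects who never received the device at surgery. |
| Further criteria to be set later | 5.2, Per Protocol list | No. They have no content yet and belong to Per Protocol only. |

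The eye is therefore a responder in the primary analysis.

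**Step 2: size.** With x responders among N eyes, the rate is x/N. Reclassifying k explanted responders gives (x − k)/N, a fall of k/N. For one eye: 1/30 = 3.3 points, 1/40 = 2.5 points, 1/100 = 1.0 point.

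**Step 3: the interval.** Section 5.3.1 says: "The exact 95% confidence interval of the response rate will be calculated based on binomial distribution". I used Clopper-Pearson: the lower limit is the 2.5% quantile of Beta(x, N − x + 1) and the upper limit is the 97.5% quantile of Beta(x + 1, N − x). N, the 70% starting rate and the number of eyes are all assumptions.

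| N | No eye reclassified | One eye | Three eyes |
|---|---|---|---|
| 30 | 21/30 = 70.0% (50.6 to 85.3) | 20/30 = 66.7% (47.2 to 82.7) | 18/30 = 60.0% (40.6 to 77.3) |
| 60 | 42/60 = 70.0% (56.8 to 81.2) | 41/60 = 68.3% (55.0 to 79.7) | 39/60 = 65.0% (51.6 to 76.9) |
| 100 | 70/100 = 70.0% (60.0 to 78.8) | 69/100 = 69.0% (59.0 to 77.9) | 67/100 = 67.0% (56.9 to 76.1) |

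The point estimate falls by 1/N per eye whatever the starting rate.

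**The case against.** The best defence is that scoring the observed 12-month outcome of everyone operated on, whatever happens in between, is a recognised treatment-policy approach. It is, but the plan never says that it takes this approach, and its SSI rule points the other way. This defence would need a statement in the plan to stand.

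A second defence is rarity. An affected eye must be explanted for a reason other than IOP, reach month 12, meet the IOP threshold and need no extra medication, in a population with refractory glaucoma. The plan also states no performance goal or hypothesis for this endpoint, so no stated decision would change. Both points stand, and they limit how much this matters.

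Three stronger readings are tempting, and the documents do not support them.

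- A reader might infer that such an eye counts as a success in the Effectiveness, ITT and Per Protocol sets alike. Per Protocol membership requires eligibility, a completed 12-month visit and no IOP-lowering adverse event, and further criteria may be added. No responder analysis in ITT or Per Protocol is specified.
- A reader might infer that explantation is the only way treatment can end. Section 7.0 defines device obstruction as a blocked flow path, and section 6.8.1 lists device migration. Either could end function without removal.
- A reader might infer that explants can be read straight from the action-taken field. Section 6.7 puts them in one category with all other surgery.

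The documents also do not say whether an explanted subject continues to month 12. Without a 12-month diurnal IOP, the eye could not be scored a responder from data, so the point concerns explanted eyes that have that measurement.

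**Conclusion.** The point holds for the primary analysis in the Effectiveness Population. Followed literally, sections 5.2 and 5.3.1 count an eye explanted for a reason other than IOP control as a responder when its 12-month diurnal IOP and medication count qualify. The gap is somewhat wider than explantation: because the SSI rule stands only under Per Protocol, the primary analysis has no stated surgical failure rule at all, even for surgery done to control IOP.

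The size per eye is 1/N, or about 3.3 to 1.0 percentage points for an assumed N of 30 to 100. The total effect is unknown because neither N nor the explant rate is given, and it is probably small. The plan should be corrected before data review. Nothing in the documents shows that the trial's conclusion would turn on it.

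**What to change.** In section 5.3.1 add a rule to this effect: *A subject whose microstent is explanted from the study eye before the 12-month diurnal IOP measurement, for any reason, is a non-responder in the Effectiveness Population and in any ITT or Per Protocol responder analysis.* State the existing SSI non-responder rule in the same place, so that it governs the primary analysis and not only Per Protocol.

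In section 5.3.2 keep explanted subjects in the analysis population and add a sensitivity summary of the mean change in diurnal IOP without values measured after explantation, giving the number of values left out.

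Record explantation with its own flag and date, or identify it by review of the adverse event details, since the action-taken category cannot separate it from other surgery.

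The cost is a few sentences in the SAP, one data item or a short review of adverse event details, and one extra summary. The response rate may be slightly lower. No clinical procedure changes.

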6.8 Serious Adverse Event and Unanticipated Adverse Device Effect Reporting

Serious Adverse Events (SAE) and unanticipated adverse device effects (UADE) must be reported to the study sponsor as soon as possible and no later than 10 working days after the investigator first learns of the event.

For initial reports, investigators should record all case details that can be gathered within the reporting timeframe. Relevant follow-up information should be submitted to the Sponsor as soon as it becomes available and/or upon request. For some events, the sponsor or its designee or the medical monitor may follow up with the site by telephone, fax, electronic mail, and/or a monitoring visit to obtain additional case details deemed necessary to appropriately evaluate the event (e.g., hospital discharge summary, consultant report, or autopsy report). Reports relating to the subject's subsequent medical course must be submitted to the study sponsor until the event has subsided or, in case of permanent impairment, until the event stabilizes and the overall clinical outcome has been ascertained.

The Sponsor will be responsible for informing regulatory authorities and all other IRBs/ECs and Investigators participating in the study of the UADE within 10 working days after notice of the event.

6.8.1 Anticipated Adverse Events

Anticipated AEs associated with glaucoma surgical procedures that might reasonably be expected to occur in this study are listed below. These specific examples of anticipated AEs include, but are not limited to:

Intraoperative Adverse Events

- Choroidal hemorrhage or effusion
- Corneal abrasion
- Corneal edema
- Cyclodialysis cleft
- Hyphema obscuring the surgeon's view
- Inadvertent perforation of the sclera
- Iridodialysis
- Lens / capsular bag damage (crystalline or IOL)
- Microstent malposition
- Significant iris injury or trauma
- Vitreous loss
- Zonular dialysis

Postoperative adverse events include

- Angle closure
- Angle recession
- Anterior chamber cell or flare requiring either an increase in the standard postoperative steroid regimen or re-initiation of steroid use following completion of the standard postoperative steroid regimen.
- Aqueous misdirection
- Atrophy, phthisis
- Best-corrected visual acuity loss of 2 lines (10 letters) or more compared to baseline on the ETDRS chart measured before or at 1-month postoperative
- Best-corrected visual acuity loss of 2 lines (10 letters) or more compared to baseline on the ETDRS chart measured after 1-month postoperative
- Blebitis
- Choroidal detachment
- Choroidal hemorrhage or effusion (detachment with at least a partially hemorrhagic component that obstructs or causes pain, including both peripheral and "kissing" choroidal detachments) lasting 30 days or less
- Choroidal hemorrhage or effusion (detachment with at least a partially hemorrhagic component that obstructs or causes pain, including both peripheral and "kissing" choroidal detachments) lasting longer than 30 days
- Chronic anterior uveitis defined as inflammation of grade 1+ or worse persisting for more than 90 days postoperatively or that recurs less than 90 days after discontinuing standard medication regimen
- Chronic pain in the study eye onset ³ 3-months postoperative
- Corneal decompensation

- Corneal edema persisting > 30 days (mild to moderate) or severe corneal edema ≥ 1 day.
- Corneal opacification
- Descemet's membrane detachment
- Device migration (dislodgement or movement)
- Device obstruction
- Elevated mean IOP ≥ 10 mmHg than the qualifying baseline mean IOP onset before or at 1-month postoperative
- Elevated mean IOP ≥ 10 mmHg than the qualifying baseline mean IOP onset after 1-month postoperative
- Endophthalmitis
- Flat anterior chamber with lens/cornea touch or shallow anterior chamber with peripheral iridocorneal apposition
- Hyphema ≥ 2 mm in height (layered) at any time
- Hyphema present or arising > 30 days postoperative
- Hypotony (defined as IOP < 6 mmHg) onset before 1-month postoperative
- Hypotony (defined as IOP < 6 mmHg) onset at or after 1-month postoperative
- Implant corneal touch
- Implant-iris touch associated with intraocular inflammation, pigment dispersion, or other sequelae
- Inadvertent bleb
- Increase in vertical C/D ratio of ≥ 0.3 units from screening on fundus examination
- Iris prolapse/wound incarceration
- Maculopathy including hypotonic maculopathy
- Persistent diplopia
- Pupil block
- Retinal complications (e.g., flap tears, retinal break, retinal detachment, age related macular degeneration, diabetic retinopathy, macular edema, epiretinal membrane, central serous retinopathy, or proliferative vitreoretinopathy)
- Scleral ectasia
- Surgical re-intervention in the study eye (other than paracentesis to relieve pressure within the 1 week visit)
- Toxic anterior segment syndrome (TASS)
- Vitreous haze
- Vitreous hemorrhage
- Vitritis
- Worsening of 2-points (from screening) to "severe" on the slit lamp examination findings (other than cells and flare) onset at or after 3-months postoperative not associated with a pre-existing condition
- Worsening of lens opacities (defined as a 2.0 or more score change on at least one category of the LOCS III grading system, at 2 or more consecutive visits)
- Worsening of visual field (mean deviation worsening by 3.0 dB or more, confirmed by 2 repeat measurements)
- Wound dehiscence (persistent aqueous leak or fistula formation)

For any adverse event that may be due to incorrect device positioning (i.e. vitreous hemorrhage, hyphema, hypotony), gonioscopy should be performed to assess the device position. If the position cannot be adequately evaluated by gonioscopy, ultrasound biomicroscopy (UBM) should be performed.

For slit lamp examination, gonioscopy and fundus findings for which there is no grading scale, any finding considered by the study investigator to be marked or severe, i.e., clinically significant, should be recorded as an Adverse Event.

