4.0 CLINICAL FOLLOW-UP SCHEDULE

All subjects will be scheduled to return for follow-up examinations at defined intervals through 12 months. **Table 5** shows the schedule of events and procedures at each protocol-required visit.

SCHEDULE OF VISITS

| Procedure | Screening ¹ | Baseline (30 days from Scr) | Surgery (30 days from BL) | 1D Postop (+/- 2D) | 7D Postop (+/- 2D) | 1M Postop (30+/- 7D) | 2M Postop (60+/- 10D) | 3M Postop (90+/- 14D) | 6M Postop (183+/- 14D) | 9M Postop (274+/- 30D) | 12M Postop (365+/- 45D) |
|---|------------------------|--------------------------------|------------------------------|-----------------------|-----------------------|-------------------------|--------------------------|--------------------------|---------------------------|---------------------------|----------------------------|
| Informed Consent | X | | | | | | | | | | |
| Medical History Ophthalmic and Non-Ophthalmic | X | | | | | | | | | | |
| Medication Assessment | X | X | X | X | X | X | X | X | X | X | X |
| Manifest Refraction | X | X | | X | X | X | X | X | X | X | X |
| BCVA - Snellen | X | | | | | | | | | | |
| Visual Acuity-Pinhole | | | X | | | | | | | | |
| BCVA - ETDRS | | X | | | X | X | X | X | X | X | X |
| Intraocular Pressure Goldmann Applanation Tonometry | | X | | X | X | X | X | X | X | X | X |
| Diurnal Intraocular Pressure Goldmann Applanation Tonometry | | | X ³ | | | | | | | | X ³ |
| Intraocular Pressure 2 to 6 hours after surgery | | | | X ⁴ | | | | | | | |
| Pachymetry CCT | X | | | | | X | X | X | X | X | X |
| Gonioscopy | X | | | | | X | X | X | X | X | X |
| Slit Lamp Exam | X | X | | X | X | X | X | X | X | X | X |
| Lenticular Opacity Grading | X ⁵ | | | | | X ⁵ | | | X ⁵ | | X ⁵ |
| Visual Field Humphrey 24-2 SITA Standard | X | | | | | | X | X | X | X | X |
| Fundus Exam/Disc Evaluation | X | | | | | | X | X | X | X | X |
| Optic Disc Photography | X | | | | | | | | | | X |
| Subject Questionnaire | X | | | | | | | X | | | X |
| Hydrus Implantation | | | | X ⁶ | | | | | | | |
| Adverse Event Assessment | | | | X | X | X | X | X | X | X | X |

¹ At the Screening Visit, all assessments will be performed for both eyes.

² At the Baseline Visit, both eyes may be evaluated if eligibility confirmed after all Screening procedures completed.

³ Daytime-Diurnal IOP measurements will be performed 3 times at 8:00 AM (± 1 hour), 12:00 PM (± 1 hour), and 4:00 PM (± 1 hour).

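### Visual field worsening needs two repeat measurements, but the scheduled fields allow two only for a loss first seen by 6 months, so a later loss can be missing from the safety tables

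*Combined protocol and SAP*

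**What the plan says.** The list of anticipated postoperative events in section 6.8.1 includes "Worsening of visual field (mean deviation worsening by 3.0 dB or more, confirmed by 2 repeat measurements". Counting the field that first shows the loss, the item needs three fields.

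The schedule in section 4.0 gives the visual field row as "Visual Field Humphrey 24-2 SITA Standard | X | | | | | | X | X | X | X | X". Its 11 cells match the 11 visit columns: one field at screening, then fields at 2, 3, 6, 9 and 12 months. The last three columns are "6M Postop (183+/- 14D) | 9M Postop (274+/- 30D) | 12M Postop (365+/- 45D". Nothing is scheduled beyond that: "All subjects will be scheduled to return for follow-up examinations at defined intervals through 12 months".

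Section 6.6 covers the period after exit. Its general rule begins "After exit from the study, ongoing AEs should be followed until resolution (with or without sequelae), stabilization, or it is determined that there is no", and it also asks for physician follow-up where there is a "significant, ocular (study eye only) adverse event at the exit visit". Both provisions start from a finding that is already an adverse event, and neither names a repeat field.

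Section 5.4 summarizes adverse events by counts and percentages. Neither section 5.3 nor section 5.4 plans a summary of mean deviation (MD) by visit, and section 5.1 makes data listings optional.

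**The concern.** The confirmation rule and the field schedule do not fit together at the end of follow-up. A rule needing two repeats cannot be met on scheduled data by a loss that first appears at either of the last two visits. The plan does not say when repeats are taken, whether they may be unscheduled, or how an unconfirmed late loss is recorded.

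Eligible eyes have refractory glaucoma and MD of -3 dB or worse (section 3.2), so loss of field is a natural safety question. The 9- and 12-month fields are collected, yet an MD loss that is not classed as an adverse event appears in no specified table. Whether it is counted may then depend on whether a site happens to repeat the field.

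**Working it through.** The plan states no event rate or count for this item, so there is no figure to reproduce. The check sets the definition against the schedule.

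**Step 1. Later scheduled fields by visit of first detection** (section 4.0), against the 2 repeats required (section 6.8.1):

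| Loss first seen at | Later scheduled fields | Two repeats possible? |
|---|---|---|
| 2M | 4 (3M, 6M, 9M, 12M) | yes |
| 3M | 3 (6M, 9M, 12M) | yes |
| 6M | 2 (9M, 12M) | yes, if both are done |
| 9M | 1 (12M) | no |
| 12M | 0 | no |

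Some rows of the table look shifted in the extracted text. That does not affect this result, because 9M is the last column but one and no shift can put two fields after it.

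**Step 2. Length of the uncovered period.** A loss arising after the 6M field is first seen at 9M or 12M. With 6M at day 183 and 12M at day 365, this is (365 − 183)/365 = 182/365 = 49.9% of follow-up. Moving the 6M field across its ±14-day window gives (365 − 197)/365 = 46.0% to (365 − 169)/365 = 53.7%.

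**Step 3. Share of true losses affected.** The documents give no onset data, so these are assumptions. Each loss persists and is seen at the next scheduled field.
- Uniform onset over 12 months: 3/12 first seen at 9M plus 3/12 at 12M = 50%.
- Exponential onset with mean m months, truncated at 12: share = (e^(−6/m) − e^(−12/m))/(1 − e^(−12/m)).
  - m = 6: (0.3679 − 0.1353)/(1 − 0.1353) = 26.9%.
  - m = 4: (0.2231 − 0.0498)/(1 − 0.0498) = 18.2%.

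**Step 4. Why unconfirmed losses need their own lines.** Take a stable eye whose MD has an assumed test-to-test SD s of 1.0 to 1.5 dB, with normal errors and one screening field as reference. (The item does not name its reference; screening is the only preoperative field scheduled.)
- One field shows a 3 dB loss with probability 1 − Φ(3/(s√2)). For s = 1.0 this is 1 − Φ(2.121) = 1.7%; for s = 1.5 it is 1 − Φ(1.414) = 7.9%.
- Given the reference error Z, each later field shows the loss with probability p = Φ(Z − 3/s). Three of three fields show it with probability E[p³] = 0.09% (s = 1.0) to 1.05% (s = 1.5).

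Confirmation therefore does useful work. For a loss absent at 2M, 3M and 6M, the same model gives these false-positive rates:

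| Pattern in a stable eye | Formula | s = 1.0 | s = 1.5 |
|---|---|---|---|
| First seen 9M, present 12M | E[(1−p)³p²] | 0.106% | 0.557% |
| First seen 9M, absent 12M | E[(1−p)⁴p] | 1.001% | 2.939% |
| First seen 12M | E[(1−p)⁴p] | 1.001% | 2.939% |
| Sum | | 2.1% | 6.4% |

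The middle row, where the 12M field contradicts the 9M one, is 1.001/2.108 = 47.5% of the sum for s = 1.0 and 2.939/6.435 = 45.7% for s = 1.5. One pooled line for losses first seen at 9M or 12M would thus be nearly half non-reproduced findings.

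**The case against.** The strongest reply is that the item asks for repeat measurements, not repeat visits. The lens opacity item just above it ties confirmation to consecutive visits, so the list names visits when it means them. Repeats at the same or an unscheduled visit fit the wording, and a definition that demands confirmation may itself prompt them. The section 6.8.1 list is also open-ended and serves to sort events as anticipated or not (section 6.4). Recording is governed by the broad definition in section 6.1 and by section 6.2, so an investigator may record a late loss without two repeats. Finally, no hypothesis or safety margin depends on this item.

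Much of this stands. A reader might infer that late field loss is bound to go uncounted, that the reported rate covers only losses first seen by 6 months, and that it therefore understates harm. The documents do not support those statements, because the other routes are open.

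What does not stand is that these routes are a reliable backstop:
- No section requires, times or triggers an unscheduled field. By contrast, section 6.8.1 does write in follow-on examinations where device position is in doubt.
- Section 6.1 excludes change consistent with natural progression, and field loss in glaucoma is an obvious candidate for that exclusion.
- The closing provision of section 6.8.1 for marked or severe ungraded findings covers slit lamp, gonioscopy and fundus findings, not fields.
- The post-exit provisions in section 6.6 start from an existing adverse event.

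**Conclusion.** The point holds as a reporting gap. On scheduled fields alone, two repeats are possible at 3 of the 5 postoperative field visits and impossible at the last 2, and this count needs no assumption. If no unscheduled repeat is done and the investigator does not record the loss under the general definition, a loss first seen at 9M or 12M appears in no specified safety table.

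The share of true losses affected is not known from the documents. The range of 18% to 50% rests wholly on the assumed onset patterns, and the upper end is simply what uniform onset implies. It is the share exposed to the gap, not the share that would be lost. The false-positive figures rest on the assumed SD of 1.0 to 1.5 dB. The primary effectiveness analysis is not affected.

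**What to change.** Keep the confirmed definition in section 6.8.1. State in section 5.4 that the safety tables also give, from fields already collected, separate counts of eyes with an MD loss of 3.0 dB or more that lack two repeats at exit:

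- (a) loss first seen at 9M and still present at 12M;
- (b) loss first seen at 12M, with no repeat.

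List 9M losses not reproduced at 12M separately, and do not count them as possible worsening. Count late losses confirmed by unscheduled repeats in the confirmed line. Footnote that line to say that scheduled fields permit two repeats only for losses first seen by 6M. A label restricting the line to losses seen by 6M would be wrong, since one late loss confirmed off schedule would make it untrue.

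The cost is a short addition to section 5.4 and a few table lines; no further field test is needed. The downside is that the unconfirmed counts contain some false positives and look less favourable. Under the noise model above, (a) and (b) together would take in 0.106% + 1.001% = 1.1% to 0.557% + 2.939% = 3.5% of stable eyes.
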